#### SPONSOR: GW PHARMA LIMITED

# **1 PROTOCOL SYNOPSIS**

Trial Title	A Double-blind, Randomized, Placebo-controlled, Parallel-group Trial of the Efficacy and Safety of Nabiximols Oromucosal Spray as Add-on Therapy in Patients with Spasticity Due to Multiple Sclerosis
Clinical Trial Type	Phase 3
Indication	Symptomatic treatment of spasticity in patients with multiple sclerosis (MS)
Primary Objective	To establish the efficacy of nabiximols relative to placebo in reducing spasm count as part of the presentation of spasticity when used as adjunctive therapy in patients with MS who have not achieved adequate relief from other antispasticity agents
Secondary Objective(s)	
 
To evaluate the effect of nabiximols relative to placebo using the following patient-reported outcome measure of spasticity: 
 
The MS Spasticity Scale (MSSS-88) total score
 
 
 
To evaluate the safety and tolerability of nabiximols
 
To evaluate the pharmacokinetics (PK) of nabiximols
 

Exploratory Objective(s)	
 
To evaluate the effect of nabiximols relative to placebo using the following patient-reported outcome measures and clinician-administered assessments of spasticity: 
 
The 8 MS Spasticity Scale (MSSS-88) subscale scores
 
The 11-point Numerical Rating Scale (NRS) for spasm severity
 
The 11-point NRS for spasticity
 
 
 
To evaluate the effect of nabiximols relative to placebo on health-related quality of life (QoL), as reflected by the 36-Item Short Form Health Survey (SF-36)
 
To evaluate the effect of nabiximols relative to placebo on functional outcome as reflected by walking ability using the Timed 25-Foot Walk (T25FW) test
 

Trial Design	
 
This multicenter, double-blind, placebo-controlled trial includes a 28-day baseline period, a 12-week treatment period (comprising a 2-week titration phase and a 10-week maintenance phase), and 2-week follow-up period.
 
Eligible patients will enter a 28-day baseline period. During baseline, patients will maintain their optimized oral antispasticity medication regimen (that must include at least 1 of baclofen, tizanidine or dantrolene) and record spasm count, 11-point NRS
 

spasm severity score, 11-point NRS spasticity score, and use of antispasticity medications once daily, around the same time of day, preferably in the evening before retiring to sleep, using an electronic daily diary. At Visit 2 (Day 1), eligible patients will be randomized to either nabiximols or placebo in a 1:1 ratio. Patients will initiate investigational medicinal product (IMP) treatment as a single spray in the evening on the first day of the titration phase. Patients will be advised to titrate IMP, beginning with 1 spray/day, to an optimized dose or to a maximum of
12 sprays/day over the first 14 days of treatment. Patients may leave a gap between sprays of approximately 15 minutes. Patients should continue at the same dose level achieved at the end of the titration phase (i.e., their daily optimized dose) $\pm$ 1 spray divided into a morning dose and an evening dose for the remainder of the treatment period. For the first 14 days of administering stable doses of IMP following titration, patients should be instructed to gradually decrease the interval between sprays to a target interval of approximately 1 minute between sprays. Patients will be advised to administer IMP at approximately the same time each day in a consistent manner in relation to food consumption. Morning and evening doses should be administered around the same time within 30 minutes after starting a snack or meal.
Daily spasm count, the patient's symptom experiences, functional outcomes, health-related quality of life, safety, tolerability, and PK will be evaluated during the treatment period.
Following randomization (Visit 2 [Day 1]), patients will attend the trial site on Visit 3 (Day 15), Visit 4 (Day 29), and Visit 5 (Day 57). The End of Treatment Visit (Visit 6) will occur on Day 85 ( $\pm$ 7 days). Participants who are permanently discontinued from receiving IMP will be recommended to continue the study and follow the original visit schedule and requirements (e.g. eDiary data entry) without taking IMP.
If a participant discontinues from the IMP and is unwilling or unable to follow the original visit schedule and requirements without taking IMP, he or she should be asked, at the discretion of the investigator, to return to the study site for the Early Withdrawal Visit (see Schedule of Assessment table). Where possible, the Early Withdrawal Visit should be within 14 days from last IMP dose, unless consent is withdrawn from further study participant, or the participant is lost to follow-up.
A Safety Follow-up Visit (Visit 7 [Day 99]) will take place 14 $(\pm 4)$ days after the End of Treatment Visit or Withdrawal Visit for all patients.

	Patients who complete the trial will participate for a total of approximately 18 weeks (127 days), including the 28-day baseline period. Patients will have a maximum duration of 85 ( $\pm$ 7) days on IMP treatment.
Primary Endpoint	Change from baseline in the average daily spasm count (from Days 57 to 84 compared to the average daily spasm count for the baseline period).
Secondary Endpoints	
 
Efficacy:
 
Change from baseline in total score of the MSSS-88 at Visit 6 Safety:
 
Frequency of treatment-emergent adverse events (AEs)
 
Change from baseline to each assessment timepoint by treatment arm for the following: 
 
Clinical laboratory tests
 
Vital signs
 
12-lead electrocardiograms (ECGs)
 
 
 
Columbia-Suicide Severity Rating Scale (C-SSRS) at screening, and at each subsequent timepoint with reference to the last assessment (since last visit)
 
Pharmacokinetics:
 
Plasma concentrations for Δ-tetrahydrocannabinol (THC) and its relevant metabolites (11-hydroxy-Δ-tetrahydrocannabinol [11-OH-THC] and 11-nor-9-carboxy-Δ-tetrahydrocannabinol [11-COOH-THC]) and cannabidiol (CBD) and its relevant metabolites (7-hydroxy-cannabidiol [7-OH-CBD]) at Visits 2 (predose), 3, 4, 5, and 6
 

Exploratory Endpoints	
 
Efficacy:
 
Change from baseline in the 8 subscale scores of the MSSS-88 at Visit 6
 
Change from baseline in average daily 11-point NRS spasm severity score to Days 57 to 84
 
Change from the last 7 days of baseline in average daily 11-point NRS spasticity score to Days 78 to 84
 
Change from baseline in the SF-36 total score at Visit 6 (Day 85)
 
Change from baseline in Timed 25-Foot Walk (T25FW) test at Visit 6 (Day 85)
 

a 1 a'	
Sample Size	The trial will consist of 2 treatment arms: a nabiximols treatment arm and a placebo treatment arm.
	446 patients (223 patients per treatment arm) will be randomized to nabiximols or placebo in a 1:1 ratio.
Summary of	Inclusion Criteria
Patient	Screening (Visit 1)
Eligibility Criteria	For inclusion in the trial, patient must fulfill ALL of the following criteria:
	• Male or female aged 18 years or above
	• Willing and able to give informed consent for participation in the trial
	• Willing and able (in the investigator's opinion) to comply with
	all trial requirements. (With the exception of the T25FW test,
	if the patient is non-ambulatory)
	• Has had a diagnosis with any disease subtype of MS, by
	revised 2017 McDonald criteria, for at least 12 months prior to
	Visit 1 and is expected to remain stable for the duration of the trial
	Has had treatment with at least 1 optimized oral antispasticity
	therapy prior to Visit 1 that must include either oral baclofen or
	oral tizanidine (monotherapy or combination therapy)
	• Currently receiving optimized treatment with at least 1 oral
	antispasticity medication (baclofen, tizanidine or dantrolene)
	and has been stable for at least 30 days prior to Visit 1.
	Despite optimization, the patient does not have adequate relief
	of spasticity signs and symptoms, including muscle spasms.
	Optimization of antispasticity medications is defined as having
	reached the most efficacious and best tolerated dose according
	to the relevant local prescribing information. The patient must
	be willing to maintain the same antispasticity medication and
	not plan to initiate a new course of physiotherapy for the
	duration of the trial
	• If currently receiving an MS disease-modifying therapy, it
	must be at a stable dose for at least 3 months prior to Visit 1
	and is expected to remain stable for the duration of the trial
	• If currently receiving dalfampridine or fampridine, it must be at a stable dose for at least 3 months prior to Visit 1 and is expected to remain stable for the duration of the trial

• Willing to allow the responsible authorities to be notified of
participation in the trial, if mandated by local law
• Willing to allow his or her primary care practitioner (if he or
she has one) and/or treating neurologist (if he or she has one) to
be notified of participation in the trial, if the primary care
practitioner/treating neurologist is different than the
investigator
Additional Inclusion Criteria at Randomization (Visit 2)
The patient is eligible for randomization in the trial if, in addition to continuing to meet the Screening (Visit 1) inclusion criteria, they also meet ALL of the following criteria during the first 28 days of the baseline period (Note: patients are expected to start completing their electronic diary in the evening of their screening visit):
• In the opinion of the investigator, the patient is able to interpret
and report spasm count data accurately
• Completed their electronic diary for at least 25 of the first
28 days of the baseline period
• Has an average daily spasm count of $\geq 4$ during the first
28 days of the baseline period, as recorded by the patient
• Has no more than 35 spasms on any single day of the first 28
days of the baseline period, as recorded by the patient
• Does not have > 7 consecutive days without experiencing any
spasm during the first 28 days of the baseline period
If, for any reason, the patient is unable to attend the site for randomization within the visit window, the site should contact the Medical Monitor or the sponsor to discuss.

ad 28	addition to meeting the Screening (Visit 1) inclusion criteria and ditional inclusion criteria above, any patient with more than days between Visit 1 and Visit 2 would need to meet ALL of e following criteria prior to randomization:
•	Completed their electronic diary for at least 85% of days between Visit 1 and Visit 2
•	Has an average daily spasm count of $\geq$ 4 between Visit 1 and Visit 2 (randomization), as recorded by the patient
•	Has no more than 35 spasms on any single day between Visit 1 and Visit 2, as recorded by the patient
•	Does not have > 7 consecutive days without experiencing any spasm between Visit 1 and Visit 2
Ex	cclusion Criteria
Th	he patient may not enter the trial if ANY of the following apply:
•	Previously participated in a clinical trial of nabiximols or has
	had a poor previous response or intolerance to nabiximols or
	other cannabinoid-containing products used for therapeutic
	purposes
•	Any concomitant disease or disorder that has spasticity-like
	symptoms or that may influence the patient's level of spasticity
•	Medical history suggests that relapse/remission is likely to
	occur during the trial, which, in the opinion of the investigator,
	is expected to influence the patient's spasticity
•	Has had a relapse of MS within the 60 days prior to Visit 1
•	Has taken cannabis, or a cannabis-derived product for
	medicinal or recreational use within the 30 days prior to
	screening (Visit 1) or a positive blood drug test for THC at
	screening (Visit 1)
•	Is unwilling to abstain from use of cannabis, or
	a cannabis-derived product for medicinal or recreational
	purposes for the duration of the trial
•	Currently using botulinum toxin injection for the relief of
	spasticity (within 6 months of Visit 1)
•	Is unwilling to abstain from the use of botulinum toxin
	injection for the relief of spasticity for the duration of the trial
•	Currently taking antipsychotic medication
	Currently taking benzodiazepines, unless the doses and dosing
	regimen have been stable for at least 30 days prior to Visit 1
	regimen nuve oven studie for ut leust 50 duys prior to visit r

•	Has any known or suspected hypersensitivity to cannabinoids
	or any of the excipients of the IMP
•	Has experienced myocardial infarction or clinically significant
	cardiac dysfunction within the 12 months prior to Visit 1 or has
	a cardiac disorder that, in the opinion of the investigator, would
	put the patient at risk of a clinically significant arrhythmia or
	myocardial infarction
•	Has a diastolic blood pressure of < 50 mmHg or > 105 mmHg
	or systolic blood pressure < 90 mmHg or > 150 mmHg (when
	measured in a supine position at rest for 5 minutes), or a
	postural drop in the systolic blood pressure of $\geq 20$ mmHg or in
	diastolic blood pressure of $\geq 10 \text{ mmHg}$ at Visit 1. All
	measurements will be performed singly and can be repeated
	once, if any are outside the reference range but not considered
	clinically significant
•	Has clinically significant impaired renal function at Visit 1, as
	evidenced by an estimated creatinine clearance lower than
	50 mL/min. All measurements will be performed singly and
	can be repeated once, if any are outside the reference range but
	not considered clinically significant
•	Has moderately impaired hepatic function at Visit 1, defined as
	serum alanine aminotransferase (ALT) or aspartate
	aminotransferase (AST) $> 2 \times$ upper limit of normal (ULN).
	All measurements will be performed singly and can be
	repeated once, if any are outside the reference range but not
	considered clinically significant
•	Male and fertile (i.e., after puberty unless permanently sterile
	by bilateral orchiectomy) unless willing to ensure that he uses
	male contraception (condom or vasectomy) or remains sexually
	abstinent during the trial and for 3 months thereafter
	6

•	Female and of childbearing potential (i.e., following menarche
	and until becoming postmenopausal for $\geq 12$ consecutive
	months with a follicle stimulating hormone (FSH)
	$\geq$ 30 mIU/mL unless permanently sterile by hysterectomy,
	bilateral salpingectomy, or bilateral oophorectomy) unless
	willing to ensure that she uses a highly effective method of
	birth control (e.g., intrauterine device/hormone-releasing
	system, bilateral tubal occlusion, vasectomized partner, other
	highly effective hormonal methods or sexual abstinence)
	during the trial and for 3 months thereafter. Patients using
	combined hormonal methods or a progestogen-only pill or
	injection or implant should use an additional barrier method
	such as a condom or diaphragm during the trial and for
	3 months thereafter
•	Female and pregnant (positive pregnancy test at Visit 1 or
	Visit 2 [predose]), lactating, or planning pregnancy during the
	course of the trial or within 3 months thereafter
•	Received an IMP within the 30 days prior to Visit 1
•	Has any other clinically significant disease or disorder
	(including seizure disorder) that, in the opinion of the
	investigator, may put the patient, other patients, or site staff at
	risk because of participation in the trial, influence the
	interpretation of trial results, or may affect the patient's ability
	to take part in the trial
•	Has any abnormalities identified following a physical
	examination, clinical laboratory, serology, or other applicable
	screen procedures that, in the opinion of the investigator,
	would jeopardize the safety of the patient or the conduct of the
	study if he or she took part in the trial
•	Has any history of suicidal behavior in the 5 years prior to
	Visit 1 or a suicidal ideation score of 3, 4, or 5 on the C-SSRS
	in the month prior to Visit 1
•	Has a history of severe psychiatric disorder that may be
	exacerbated by the use of a cannabinoid-containing product
•	Has donated blood during the 3 months prior to Visit 1 and is
	unwilling to abstain from donation of blood during the trial
•	Has been previously randomized into this trial

• Has any known or suspected history of alcohol or substance
use disorder within 1 year prior to Visit 1. Patients with
nicotine use disorder are allowed to enroll
• Currently using an illicit drug or current nonprescribed use of
any prescription drug. A positive drug test at Visits 1 or 2 for a
prescribed medication is not exclusionary at the investigator's
discretion. A positive drug test at Visit 1 or predose at Visit 2
for illicit drugs may be repeated locally at the investigator's
discretion
• Has any planned clinical interventions or intends to change any
or all medications that may have an effect on spasticity or MS
during the trial
• Currently taking drugs that are solely metabolized by UGT1A9
and UGT2B7
• Currently taking strong CYP3A4 inducers (e.g., rifampicin,
carbamazepine, phenytoin, phenobarbital, St John's Wort)
• There is an expectation that the participant will require a new
course of treatment with strong CYP3A4 inhibitors during the
study duration (e.g., participant with recurrent fungal infections
requiring intermittent treatment with itraconazole)
• Patients who receive a positive coronavirus disease 2019
(COVID-19) antigen test result, potentially suggesting
infective status, before randomization may be screen failed, at
the discretion of the investigator
Individuals who do not meet the criteria for participation in this
trial (screen failure) because of, for example, fever due to a brief
acute upper respiratory illness, having taken a prohibited over the
counter medication within the excluded period, recent blood
donation, due to the inclusion criterion related to the ability to
interpret and report spasm count data accurately, or who could not
be randomized for logistical reasons, can be rescreened once, at the
discretion of the investigator or designee, with sponsor approval.
Rescreened participants should be assigned a new screening number.

Criteria for	The patient must be withdrawn from the trial if any of the
Withdrawal	following apply:
	• Administrative decision by the investigator, GW Pharma Ltd,
	or regulatory authority
	• Withdrawal of patient consent
	• Lost to follow-up
	The patient must cease IMP and should remain in the trial if any of the following apply:
	• Pregnancy
	• Protocol deviation that is considered to potentially compromise
	the safety of the patient
	• Suicidal behavior, or a suicidal ideation score of 4 or 5 during the treatment period, as evaluated with the C-SSRS
	• ALT or AST > $3 \times$ ULN with the appearance of fatigue,
	nausea, vomiting, right upper quadrant pain or tenderness,
	fever, rash, and/or eosinophilia (> 5%)
	• ALT or AST $> 5 \times$ ULN
	• ALT or AST > 3 × ULN and (total bilirubin [TBL] > 2 × ULN
	or international normalized ratio [INR] > 1.5)
	• Any prohibited medication after Visit 1
	The patient may be required to cease IMP at the discretion of the investigator and should remain in the trial for any of the following reasons:
	• Did not meet eligibility criteria
	Patient noncompliance
	• AE (including clinically significant laboratory result) that, in
	the opinion of the investigator, would compromise the
	continued safe participation of the patient in the trial
	• Any evidence of drug abuse or diversion
	• Disease progression (defined as a relapse of MS requiring a
	change in treatment)
	
 
A positive COVID-19 test result after randomization
 

T (* .* 1	
Investigational Medicinal Product: Formulation, Mode of Administration, Dose and Regimen	Nabiximols oromucosal spray (GW-1000-02) is a mixture of THC and CBD extracts derived from Cannabis sativa L. Each of the botanical extracts contains a cannabinoid as the major constituent (i.e., THC or CBD) and minor constituents, including other cannabinoid and noncannabinoid plant components, such as terpenes, sterols, and triglycerides. Nabiximols is presented as an oromucosal spray containing THC (27 mg/mL):CBD (25 mg/mL), dissolved in ethanol:propylene
	glycol (50% v/v) excipients with peppermint oil (0.05% v/v) flavoring. Each 100 $\mu$ L spray delivers 2.7 mg THC and 2.5 mg CBD.
	Placebo to match nabiximols is presented as an oromucosal spray containing the excipients ethanol and propylene glycol (50% v/v) with colorings and flavored with peppermint oil (0.05% v/v). Each spray delivers 100 $\mu$ L containing no active ingredients.
	Treatment will be initiated as a single spray in the evening on the first day of the titration phase (normally the day of Visit 2 [Day 1]). Patients will be advised to administer IMP at approximately the same time each day in a consistent manner in relation to food consumption. Morning and evening doses should be administered around the same time within 30 minutes after starting a snack or meal. Patients will gradually titrate their daily dose by 1 additional spray/day to an individually determined optimized dose, balancing efficacy and tolerability, or to a maximum number of 12 sprays/day. Patients may leave a gap between sprays of approximately 15 minutes.
	Patients should complete titration within 14 days of their first dose of IMP and should continue at the same dose level achieved at the end of titration (i.e., their daily optimized dose) $\pm$ 1 spray divided into a morning dose and an evening dose for the remainder of the treatment period. For the first 14 days of administering stable doses of IMP following titration, patients should be instructed to gradually decrease the interval between sprays to a target interval of approximately 1 minute between sprays.
	The total daily dose should be administered as a morning dose and an evening dose, which may be composed of a different number of sprays. Patients may take their morning dose spread out during the morning and their evening dose spread out during the evening, with a minimum interval between sprays as specified above (i.e., 15 minutes during the titration phase and a target of approximately 1 minute during the maintenance phase).
Control Arm	The control arm will receive matching placebo (excipients alone).

Procedures	Assessments/procedures include the following:
	• Informed consent, demographics, previous cannabis use,
	medical history, and electronic diary training (Visit 1)
	• Eligibility check and urine drug screen (Visit 1 and 2)
	• Blood THC test (Visit 1)
	• Randomization, urine pregnancy test (if appropriate), and IMP dosing training (Visit 2 [predose])
	• Concomitant medications review, AE review, and vital signs measurement (Visits 1 through 7)
	• Physical examination (including height measurement at Visit 1 only) (Visits 1, 2 [predose], and 6)
	• Examination of oral mucosa and C-SSRS assessment (Visits 1 through 6)
	• Body weight measurement, 12-lead ECG, and clinical
	laboratory blood sampling (hematology and biochemistry) (Visits 1, 2 [predose], 4, and 6)
	
 
Dipstick urinalysis and serum pregnancy test (if appropriate) (Visits 1 and 6)
 

	
 
PK blood sampling – patients can choose the sparse PK sampling option or the semi-intensive PK sampling option: 
 
Sparse option (Visit 2 [predose], and one sample will be collected at any time during Visits 3, 4, 5, and 6)
 
Semi-intensive option (Visit 2 [predose] and at just one of Visits 3, or 4, or 5 but not during Visit 6, at predose [collected upon arrival], and then at 2, 4, and 6 hours postdose during the clinic visit).
 
 
 
MSSS-88 assessment (Visits 2 [predose], 5, and 6)
 
T25FW test in ambulatory patients, and SF-36 assessment
 

	
 
(Visits 2 [predose] and 6)
 
Medication Use Survey (Visit 6)
 

	• IMP dispensing (Visits 2 [predose], 3, 4, and 5)
	• IMP collection and compliance review (Visits 3, 4, 5, and 6)

	Electronic Detiont Diamy
	Electronic Patient Diary Patients will complete their electronic diary once daily, around the same time each day, during the baseline period prior to Visit 2 and throughout the trial until Visit 7, unless otherwise indicated, and the following assessments will be conducted:
	• Spasm count
	• 11-point NRS for spasm severity
	• 11-point NRS for spasticity
	Use of antispasticity medications
	• IMP dosing record (Visits 2 through 6)
	• Dosing in relation to food intake (applicable only to the days preceding Visits 3, 4, 5, and 6)
	• Additional procedures to screen for the presence of or immunity against infectious diseases may be conducted according to local guidance and policy. In cases where patients are not able to attend study visits due to the presence of an infectious disease or other transmissible condition (such as
	COVID-19/other pandemic restrictions), the investigator will discuss with the Sponsor potential mitigation approaches.
Statistical Considerations	The primary and secondary endpoints will be compared between treatment arms, using appropriate statistical methods, through the 12-week double-blind treatment period. Statistical hypothesis testing will be 2-sided and carried out at the 5% level of significance.
	To control for Type 1 error, the primary endpoint and secondary efficacy endpoints will be tested hierarchically, starting with the primary endpoint, then the change from baseline in total score of MSSS-88. No additional adjustments for multiplicity will be made for the exploratory endpoints. Safety data will be summarized using appropriate statistical
	methods.

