#### SPONSOR: GW PHARMA LIMITED

## Table 2-1

#### **Objectives and Endpoints**

### **Primary Estimand:**

The primary estimand for this study is defined by the following 3 components:

- Target population: patients with spasticity due to MS who have not achieved adequate relief from other antispasticity agents but have optimized treatment
- Endpoint: change from baseline in average daily spasm frequency count (from Days 57 to 84 compared to the average daily spasm count for the baseline period)
- Measure of intervention effect: mean difference in change from baseline between patients randomized to nabiximols compared to patients randomized to placebo, regardless of treatment compliance and change of other antispasticity medications; following a treatment policy strategy for handling intercurrent events.

All randomized patients and all measurements collected after treatment discontinuation and after change in antispasticity medication will be included in the primary analysis.

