# 9.1.4 Visit 6 (Day 85, End of Treatment Visit/Withdrawal Visit)

This visit will occur 84 days after the first dose of IMP or earlier, if the patient withdraws from the trial. A visit window of  $\pm$  7 days from the scheduled visit date is permitted, but it is preferred that the visit is performed on the scheduled visit day, where possible.

Patients who discontinue IMP treatment early will be encouraged to continue (off treatment) in the trial and to complete all remaining trial procedures to Visit 6 (Day 85), where possible.

The following assessments/procedures will be performed:

- Concomitant medications review
- AE review
- Physical and oral mucosa examinations
- Body weight measurement
- Vital signs measurement
- 12-lead ECG
- Clinical laboratory blood sampling (hematology and biochemistry)
- PK blood sampling (see Section 9.2.12.1)
- Dipstick urinalysis
- Serum pregnancy test (if appropriate)
- MSSS-88 assessment
- C-SSRS assessment
- T25FW test

V1, 24Sep15

- Medication Use Survey (MUS [Section 9.2.15.5])
- SF-36 assessment
- IMP collection and compliance review

Patients should be reminded to record their spasm count, 11-point NRS spasm severity score, 11-point NRS spasticity score, and use of antispasticity medications in the electronic diary once daily, around the same time of the day, preferably in the evening before retiring to sleep.

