#### 12.7 Follow-up Procedures for Adverse Events

The investigator may be asked to provide follow-up information to the GW PVD for any AEs reported or during the investigation of potential safety issues. Such requests for additional safety information may occur after Visit 7, after the trial.

AEs considered related to the IMP by the investigator or the sponsor should be followed up until resolution or the event is considered stable.

It will be left to the investigator's clinical judgment whether or not an AE is of sufficient severity to require the patient's discontinuation of treatment. A patient may also voluntarily withdraw from treatment due to what he or she perceives as an intolerable AE. Further details of withdrawal are presented in Section 10. If either of these occurs, the patient must undergo an end of treatment assessment and be given appropriate care under medical supervision until symptoms cease or the condition becomes stable. If a safety concern is identified following withdrawal of a patient, GW may contact the investigator for additional follow-up information.

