# 13.1 Sample Size, Power, and Significance Levels

446 patients will be randomized to the nabiximols or placebo treatment arms on a 1:1 basis.

The following assumptions have been used for the sample size:

- Common standard deviation of 6.5 for the change from baseline in average daily spasm count for nabiximols and placebo treatment arms
- True mean difference of -2 between the mean change from baseline in average daily spasm count in the nabiximols treatment arm compared to the placebo treatment arm

Using the above assumptions, the total sample size of 446 patients (223 patients per treatment arm) will have 90% power to detect a difference between treatment arms in change from baseline in average spasm count of -2 using a 2-sided hypothesis test at the 5% significance level.

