#### SPONSOR: GW PHARMA LIMITED

Total score of MSSS-88 will be analyzed using the MMRM methods used for the primary endpoint described in Section 13.6.1, using visit instead of period. Patients who withdraw from the trial are required to complete the procedures scheduled for Visit 6 at the time of withdrawal. For these patients, their Visit 6 data will be assigned to the nearest post-baseline Visit (for which the assessment is scheduled to be performed) based on the trial day of the visit. Further details will be specified in the SAP.

To control for Type 1 error, the primary endpoint and secondary efficacy endpoint will be tested hierarchically, starting with the primary endpoint, then the change from baseline in total score of MSSS-88. No additional adjustments for multiplicity will be made for the exploratory endpoints.

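### Patients who stop IMP and decline the full schedule have no written diary-only step, and the documents disagree on whether their exit visit is optional

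*Protocol*

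**What the plan says.** **Continuing after IMP stops.** The Synopsis and Section 4.1 recommend that a patient who stops IMP stay on the original schedule, with eDiary entry named as part of it. For anyone who does not, the rule reads: "unwilling or unable to follow the original visit schedule and requirements without taking IMP, he or she should be asked, at the discretion". The discretion is the investigator's, and the request is to attend an Early Withdrawal Visit, where possible within 14 days of the last dose. Section 9.1.4 is softer: patients who stop early are encouraged "to complete all remaining trial procedures to Visit 6 (Day 85), where possible". Section 10 says that patients who cease IMP should remain in the trial.

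**Diary.** Section 9.2.14 runs the diary to Visit 7. On the exit path, Visit 7 falls 14 (± 4) days after the Withdrawal Visit (Sections 4.1 and 10).

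**Estimand.** Table 2-1 sets a treatment-policy estimand in which "all measurements collected after treatment discontinuation and after change in antispasticity medication will be included in the primary analysis".

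**Exit visit elsewhere.** Section 13.6.2: "Patients who withdraw from the trial are required to complete the procedures scheduled for Visit 6 at the time of withdrawal". Section 12.7, for stops caused by an adverse event: "the patient must undergo an end of treatment assessment". A footnote to SAP Table 10.2-1 takes Visit 6 as completed for patients who withdraw permanently.

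**The concern.** There are two separate issues, and they touch different endpoints.

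**Primary endpoint.** The spasm count needs no site visit. A patient who will not or cannot travel could still enter a daily count at home, yet the one written fallback leads to an exit visit, and the diary stops about two weeks later. A treatment-policy estimand depends on data collected after IMP stops. When the Days 57 to 84 value is absent, the MMRM relies on missing-at-random information from patients still observed in the same arm, who may mostly be on treatment. The sample size has no allowance for such losses, withdrawn patients are not replaced, and the SAP addendum (Table 7-1) drops the sensitivity analyses, including the placebo-based imputation and tipping-point work. The reported primary result would then rest on missing at random without a planned check.

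**MSSS-88 and safety.** If the exit visit is left to discretion, whether these data exist may depend on the investigator and on how the patient is doing. The analysis text is written as though they always exist.

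**Working it through.** **1. The plan's sample size.** Inputs from Section 13.1: "True mean difference of -2 between the mean change from baseline in average daily spasm count" between arms, SD 6.5, 223 per arm, "using a 2-sided hypothesis test at the 5% significance level"; stated result: "will have 90% power to detect a difference between treatment arms".

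- Normal formula: n = 2(1.96 + 1.2816)² × 6.5² / 2² = 222 per arm.
- Noncentral t: 89.9% power at 222 per arm and 90.0% at 223.

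The stated 446 is reproduced with nothing added for dropout.

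**2. When is the Days 57 to 84 average evaluable?** Let L be the last diary day, with complete entry up to then. Days observed = L − 56; trailing missing days = 84 − L.

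- Protocol 13.6.1 needs at least 15 observed days and fewer than 10 consecutive missing days: L ≥ 71 and L ≥ 75, so L ≥ 75.
- SAP 10.17 sets the value to missing only when there are fewer than 15 observed days and also at least 10 consecutive missing days, so L ≥ 71 is enough.

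**3. Which stopping days fail on the exit path?** Let s be the day of the last dose. No diary entry is made for the day of Visit 7 (Appendix 1, note 7), so L is the day before it. Visit 7 is taken as 14 days after the exit visit.

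| Exit visit | L | Evaluable from (protocol) | Evaluable from (SAP) |
|---|---|---|---|
| Same day as last dose | s + 13 | s ≥ 62 | s ≥ 58 |
| 14 days after last dose | s + 27 | s ≥ 48 | s ≥ 44 |

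The ± 4 day window on Visit 7 shifts each cut-off by up to 4 days either way. A patient who stops at the end of titration (Day 14) reaches at most L = 14 + 27 = 41, or 45 with the window, so has no diary day in the primary period.

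This reading favours the plan. SAP 10.2.2 ends the randomized period on the day of the early withdrawal visit. If that excluded later diary days, L would be s or s + 14 and every cut-off would move 13 days later.

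**4. Illustrative power.** No withdrawal rate is documented, so the missing share d is assumed. Power = Φ(2 / (6.5 × √(2/m)) − 1.96), with m = 223(1 − d).

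| Assumed d | m per arm | Power |
|---|---|---|
| 0% | 223 | 90.1% |
| 5% | 211.8 | 88.6% |
| 10% | 200.7 | 86.9% |
| 20% | 178.4 | 82.8% |

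These are complete-case figures. The MMRM also uses baseline and the earlier 28-day periods, so its loss is probably smaller.

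**5. The exit-visit wording side by side.**

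| Place | Status of the exit assessment |
|---|---|
| Synopsis, 4.1 | Asked for at investigator discretion |
| 12.7 | Mandatory after a stop for an adverse event |
| 13.6.2 | Required of all who withdraw; used for MSSS-88 visit assignment |
| SAP Table 10.2-1 | Taken as completed |

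Under SAP Table 10.2-1 an MSSS-88 from Days 2 to 71 is assigned to Week 8 and one from Days 72 to 92 to Week 12.

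**The case against.** The strongest reply is that the protocol already wants these patients kept. The recommended path retains the diary, and its data enter the primary analysis. Section 10 lists only three grounds for mandatory withdrawal (administrative decision, consent withdrawal, loss to follow-up), and declining site visits is not one. The wording of 9.1.4 leaves room for partial participation. All of this stands. A reader might infer that primary data are lost for everyone who stops IMP; the documents do not support that. Some late stoppers on the exit path also remain evaluable. What remains is that permission is not an instruction: the specific text for a patient who declines the schedule points only to the exit visit.

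Three other inferences go too far.

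- **Remote contact only for infectious disease or a pandemic.** Section 9.1.2 allows optional telephone calls during titration, and Section 11 gives COVID-19 as an example of special circumstances.
- **Diary-only follow-up loses no site safety data compared with withdrawal.** The Visit 6/Withdrawal procedures include laboratory tests, ECG, vital signs, C-SSRS and oral examination, so a diary-only step that replaced the visit would lose them.
- **A count of primary endpoints that could be recovered.** That needs both a withdrawal rate and the share of leavers who would keep the diary; neither is documented.

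It is also fair that most early exit MSSS-88 scores would not be the tested Week 12 value. They inform it only through the MMRM.

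**Conclusion.** The point holds as a gap in instruction plus a contradiction.

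**Gap.** Obtainable Days 57 to 84 counts may be lost for exit-path patients who stop before about Day 48 to 62 under the protocol rule, or Day 44 to 58 under the SAP wording. This assumes complete diary entry to the day before Visit 7, and an exit visit between 0 and 14 days after the last dose. If the investigator does not ask for the exit visit, the text leaves the timing of Visit 7, and so the end of the diary, undefined. The size cannot be derived from the documents. The fall from 90% to about 87% or 83% rests on assumed 10% or 20% missingness, a complete-case test and the planned 223 per arm. The addendum says that enrolment stopped short of that number, so these figures describe the design and not the data in hand.

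**Contradiction.** The status of the exit visit differs between the sections named and must be reconciled. It affects MSSS-88, T25FW, SF-36 and safety, not the spasm count.

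This is something the sponsor should correct, with medium confidence; it does not invalidate the primary analysis.

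**What to change.** **(a) Synopsis and 4.1.** State that a patient who stops IMP and declines further site visits is asked to continue the eDiary to Day 84 and remains on study for the primary analysis. State also that the patient is still asked for the Early Withdrawal/Visit 6 assessments, including MSSS-88 and safety. The diary step then adds to the exit visit and does not replace it.

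**(b) Exit-visit wording.** Reconcile the Synopsis, 4.1, 12.7, 13.6.2 and SAP Table 10.2-1 so that they give the exit visit one status. Note in the analysis text that an exit MSSS-88 on Days 2 to 71 is a Week 8 value.

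**Cost.** Amendment wording, longer use of the diary device, and site reminders for a few patients. With enrolment closed, the wording matters mainly for any reuse of this design.
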